Risks attributable to behavioral testing: The questionnaires employed as part of the study may cause some subjects to feel frustrated, bored or upset. It might also cause them to feel dysphoric as it may remind them of their clinical depressive symptoms. Subjects will be told that they may stop at any time during the testing.

Possible risks of delaying treatment in MDD subjects: MDD subjects may or may not have a treating psychiatric provider during their participation. If the subject does have a current provider, the PI will correspond directly with the subjects' psychiatric provider after seeking formal permission from the subject to do so (in the form of a signed medical release form to discuss his/her care supplied by said provider's office). This will allow the PI to (1) discuss maintenance strategies for the subject during their pre-treatment phase, (2) report worsening of the patient's mood to the provider and (3) receive reports from said provider about clinical deterioration. Maintenance strategies might include, for example, having MDD subjects undergo brief interpersonal therapy (IPT), either through the outpatient Psychiatry department at BWH or directly with their provider.

However, in some cases an MDD subject may refuse to have a psychiatric provider and refuse to undergo treatment for their depression (even after the risks of doing so are explained to them by the PI). That is, they may have decided to not pursue pharmacotherapy or psychotherapy to treat their depression. In these cases, treatment would not be "delayed," as the subject never intended it to be started. For these subjects, the PI (a board certified psychiatrist) will still monitor MDD subjects in the following ways to assess symptom worsening during their study participation. First, he will directly ask subjects at each of their three visits about possible symptom worsening. Secondly, and more objectively, this will be assessed by performing a HAMD questionnaire at each of the three study visits. Third the PI will provide brief patient education on Major Depression, specifically with respect to common symptomatology, theories as to the biological basis of the disorder and treatment options. Fourth, the PI will encourage that they seek treatment in the form of psychotherapy during the study and with psychotherapy and/or pharmacotherapy after their study participation ends.

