In addition, subjects with MDD who experience a 20 percent increase in their HAMD rating scores during the course of the study will be removed from the study and referred to a regular psychiatric clinician for the institution of prompt treatment. As mentioned, this will be assessed by performing a HAMD at each of the three study visits.

Depressed patients will be evaluated at each study visit with the Columbia Suicide Severity Rating Scale (CSSRS) as well as the HDRS. If subjects report active suicidal ideation (SI) on either scale they will be removed from the study. Of note, this course of action will be taken if a subject endorses active suicidal ideation at any visit, even if their HDRS score has not increased by 20% from their last visit. Suicide risk in these individuals will be further probed by examining their CSSRS responses. If the risk of suicide is deemed high and/or imminent (e.g., if the subject endorses frequent active SI, has intent and/or plan for self-injury) the subject will be immediately referred to the Emergency Department at MGH. In these cases of extreme concern, subjects will be taken to the ED with a security escort and may have to be taken against their will. If the subject is determined to have SI but to not be an imminent risk for suicide, it will be suggested that they contact the Boston Emergency Services Team (BEST), which is jointly operated through MGH and Boston University and which is well equipped to provide acute care and to facilitate rapid referrals to psychiatric providers. Information on contacting the BEST team will be provided on the MDD resource sheet. Obviously, if the subject has an established psychiatric provider, they will be encouraged to contact that individual immediately as well.

VIII. POTENTIAL BENEFITS

It is not expected that individuals participating in this study will benefit directly from it, other than through financial compensation. Furthermore, MRI scans being used are NOT sufficiently clinically diagnostic to detect pathology. However, if a pathological finding is suspected, the subject will be referred for further neurological and/or radiological work-up.

This work will better elucidate how intrinsic networks and their dynamics are altered in MDD. It will also assess how rTMS, or other neuromodulatory strategies, create the formation of more adaptive configurations. In turn, this will pollinate future trials that optimize MDD treatments through selective targeting of intrinsic networks.

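### Subjects removed for active suicidal ideation but not sent to the emergency department are only advised to seek care, whereas a 20% HAMD rise requires a referral

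*Protocol*

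**What the plan says.** The rules stand in Protocol section VII (Risks and Discomforts), in the paragraphs on delaying treatment in MDD subjects. There are two triggers for removal.

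- **Score rise.** A subject whose HAMD score rises by 20% "will be removed from the study and referred to a regular psychiatric clinician for the institution of prompt treatment".
- **Active suicidal ideation (SI)** on the Columbia scale or the HDRS. The subject is removed whether or not the score has risen by 20%.

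The SI trigger then splits by risk. "If the risk of suicide is deemed high and/or imminent", the subject goes at once to the emergency department (ED). The examples given there are frequent active ideation, intent, or a plan. "If the subject is determined to have SI but to not be an imminent risk for suicide", then "it will be suggested that they contact the Boston Emergency Services Team (BEST". That service is described as "well equipped to provide acute care and to facilitate rapid referrals to psychiatric providers", and its contact details are on a resource sheet. Of subjects who already have a provider, the text says "they will be encouraged to contact that individual immediately as well".

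Three other provisions bear on the point:

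- Earlier in section VII, the PI may report worsening mood to a current provider once the subject has signed a release.
- For subjects who refuse a provider, "the PI will encourage that they seek treatment in the form of psychotherapy during the study and with psychotherapy and/or pharmacotherapy" once participation is over.
- Section IX has adverse events medically evaluated where that is judged appropriate, and lists referral among the possible steps.

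**The concern.** Active SI is an exclusion at entry (section III.A), so SI reported later is a new event, and the Protocol treats it as serious enough to end participation. Yet for the tier below the ED the prescribed hand-off is weaker than the one for a score rise. One subject is referred for prompt treatment; the other is given advice and a contact sheet.

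What is at stake is the safety of subjects with nobody else to turn to. The recruitment paragraph in section III targets people not being treated for the current episode, section III.A recruits unmedicated patients, and section VII expects some to refuse a provider altogether. Visit-based monitoring and adverse event collection both stop when participation ends, so what is arranged at removal matters more than it would at an ordinary visit.

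**Working it through.** No published figure is at issue, so the check sets the pathways side by side and looks for a clause that closes the gap.

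| Trigger for removal | Required action besides removal | Who must act |
|---|---|---|
| 20% HAMD rise | Referral to a psychiatric clinician for prompt treatment | Not stated, but the referral is required |
| Active SI, high and/or imminent risk | Immediate ED referral, with escort in extreme cases | The study |
| Active SI, otherwise, no 20% rise | Suggestion to contact BEST; encouragement to contact a provider, if there is one | The subject |

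**1. Does the HAMD referral carry over to SI?** The sentence extending the SI rule to subjects without a 20% rise refers back to a course of action. The sentence just before it states one action only, removal. The natural reading is that removal carries over and referral does not. A subject who meets both triggers does get the referral through the HAMD rule, so the point is limited to subjects without a 20% rise.

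**2. Can SI arise without that rise?** Yes, and the Protocol says so. For example, a subject entering at the minimum HDRS of 18 needs 18 × 1.20 = 21.6, that is 22 in whole points, to trigger the HAMD rule. With active SI and a total of 21, that rule is not met.

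**3. Does another clause require a referral?**
- The PI's report to a provider needs an existing provider and a signed release, and is a report of worsening, not a referral.
- The encouragement given to subjects who refuse a provider leaves the step to them.
- The adverse event clause in section IX could cover new SI, but it is discretionary and is not tied to SI or to removal.

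So a referral is permitted, but nowhere required.

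**4. Who is left?** The ED branch takes high or imminent risk, with frequent SI, intent or plan as its examples. What remains is broadly SI that is infrequent and without intent or plan, in a subject whose score has not risen by 20%. Within that group the gap falls mainly on those without a provider.

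**5. Is the choice of verb incidental?** The Protocol uses the language of referral for the score rise, for the ED branch and, in section VIII, for a suspected finding on the scan, where "the subject will be referred for further neurological and/or radiological work-up". The lower SI tier is the exception.

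**6. Size.** The plan has 25 MDD subjects, each removable once. Without replacement of removed subjects, 25 is the ceiling. The affected subjects must meet several conditions together (SI below the ED tier, no 20% rise, and mainly no provider), and the Protocol gives no rate for any of them. The number is small but cannot be estimated.

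**The case against.** The strongest case on the other side is that the tiered response already works and the difference is mostly one of verb. The HAMD rule does not say who makes the contact, so being referred there might amount to being told where to go. The lower SI tier also names a destination, arguably a more urgent one than a regular clinician. The cases that would worry a clinician most are already in the ED branch. Section IX gives the PI, a board-certified psychiatrist, room to refer. Subjects without a provider are described as having refused one and refused treatment, so a referral may add little. The resource sheet is not available, so what the subject receives cannot be fully judged. The back-reference in the SI sentence could also be read as taking in the HAMD referral.

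Much of this stands. A reader might infer that the Protocol leaves suicidal subjects with no response, or that the study has no route to refer them. The text supports neither: BEST, the provider contact and the discretionary clause are all there. Nor can one infer that the HAMD rule obliges the PI to make the appointment.

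A reader might also fear that high but not imminent risk falls into the lower tier, because that tier is worded only in terms of imminence. This is not a working defect, since the ED branch comes first and expressly includes high risk.

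What survives is that the HAMD action is required, names a clinician and states prompt treatment as its purpose, while the lower SI action does not require any hand-off by the study. The alternative reading of the back-reference is possible but weaker, because removal is the nearer antecedent. That a subject may decline is no reason not to offer.

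**Conclusion.** The point holds in a limited form. For an MDD subject removed for active SI, not sent to the ED and without a 20% HAMD rise, the Protocol prescribes advice where a score rise brings a required referral, and no other section requires one. This is an uneven safety rule and a cheap improvement to make. It is not a gap in the care of high-risk subjects.

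No estimand, analysis, sample size or eligibility rule is touched, and a statistical analysis plan would not be the place to settle it. One might be tempted to attach an assumed event rate and quote a chance of at least one case, but nothing in the Protocol supports any rate, so the point should not rest on such a figure.

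The conclusion assumes that the back-reference in the SI sentence carries over removal only, that the ED examples fairly indicate where the line between tiers lies, and that the resource sheet, which is not available, contains no referral commitment of its own.

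**What to change.** Amend the sentence on non-imminent SI in section VII. Every subject removed for active SI and not sent to the ED is also referred to a psychiatric clinician for prompt treatment, on the same terms as under the HAMD rule. If the subject agrees, the PI makes the contact, whether with BEST, a clinician or the existing provider (with the signed release already foreseen for the last). Keep the advice about BEST and the resource sheet.

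The cost is a small wording change and a little PI time for a few subjects, using services the Protocol already names. Some will decline. If the PI would refer such subjects anyway, the amendment only records that practice.
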